#### **7.4.1.2 Sensitivity Analyses of Primary Endpoint**

The following sensitivity analyses will be performed for the primary efficacy endpoint to assess the robustness of the primary analysis.

##### **Discontinuation-reason based multiple imputation**

The MMRM analysis that will be used to perform the primary analysis of the primary endpoint assumes that missingness is at random. That is, the model assumes that the trajectory of mean daily average pain scores over time for subjects who withdraw is similar to the trajectory for those observed in their own treatment arm which is valid so long as that assumption is reasonable.

Discontinuation-reason based multiple imputation (MI) will be used to examine the sensitivity of the primary analysis results to departures from that underlying assumption and will assess a situation where data for subjects who discontinue early follow a pattern which is missing not at random. Specifically, MI will be used for imputation of any missing data, using “Jump to Reference” algorithm (where placebo is the reference group) [Carpenter et al. 2013] for subjects who discontinue due to lack of efficacy or AEs and standard regression-based MI for subjects with missing data for other reasons. The analysis will be implemented using the general three-step process (imputation phase, followed by analysis phase, followed by pooling phase) described in O’Kelly and Ratitch, 2014.

1. The imputation phase will implement MI via sequential modelling for both the “Jump to Reference” algorithm and standard regression-based MI. In particular, when implementing the “Jump to Reference” algorithm via sequential modelling, this means that only baseline values are used in the imputation of missing values for subjects in the ASP8062 30 mg once daily group who discontinue due to lack of efficacy or AEs (this variation of the “Jump to Reference” algorithm is also referred to as the “Unconditional Reference” approach). The imputation phase will generate  $M$  imputed datasets, where  $M=100$ .
2. The analysis phase will perform the primary MMRM analysis model of the primary efficacy endpoint as described in Section 7.4.1.1 for each of the  $M=100$  imputed datasets (which now contain complete data, where missing data have been filled in).
3. Rubin’s rules will be used to generate an overall set of pooled results which combines the analysis results from the  $M=100$  imputed datasets.

The overall set of pooled results will present:

- Least squares (LS) mean estimates, SE and 2-sided 90% confidence interval (CI) for mean change from baseline to Week 8 within a treatment group (ASP8062, placebo),
- The difference in LS means for ASP8062 versus placebo, SE for the difference and 2-sided 90% CI for the difference at Week 8,
- One-sided p-value for ASP8062 versus placebo at Week 8, obtained using the difference in the LS means.
- Descriptive summary statistics at Week 8 will be derived using the mean of the  $M=100$  imputed datasets.

Descriptive summaries and plots will be used to explore the pattern of missingness are described in Section 7.2.1

### **Modified baseline observation carried forward**

Prior to any analysis mBOCF will be used to impute any missing Week 8 data. Modified baseline observation carried forward is defined as imputation by BOCF for subjects who discontinue due to lack of efficacy or AEs, and imputation by LOCF for subjects with missing data at Week 8 for other reasons. The imputed change from baseline to Week 8 data will be analyzed using ANCOVA with treatment group and center (pooled site) as fixed effects and baseline value as a covariate.

The ANCOVA will present LS mean estimates, SE for the LS means and two-sided 90% CI for change from baseline to Week 8 within a treatment group (ASP8062, placebo). For comparisons between ASP8062 and placebo for the change from baseline to Week 8, the ANCOVA model will present the difference in LS mean estimates, SE and corresponding 2-sided 90% CI. The differences in LS mean estimates will be used to obtain 1-sided p-values for ASP8062 versus placebo.

### **Per-protocol analysis**

The same analysis of the primary efficacy endpoint as described in Section 7.4.1.1 will be repeated using the PPS.

#### **7.4.1.3 Subgroup analysis**

The subgroup analysis of the primary efficacy endpoint is described in Section 7.8.1

#### **7.4.2 Analysis of Secondary Endpoints**

Analysis of secondary efficacy endpoints will be performed on the FAS. Analyses of select secondary endpoints will be performed on the PPS as specified in Table 19

**Table 19 Summary of the Analyses for the Secondary Efficacy Variables**

Variable	Imputation	Analysis Set	Analysis Type
Percentage of subjects achieving $\geq 30\%$ (or $\geq 50\%$ ) reduction from baseline to Week 8 in mean daily average pain score assessed by NRS where all subjects with missing Week 8 data are classified as non-responders	BOCF	FAS	Fisher's exact test
Percentage of subjects achieving $\geq 30\%$ (or $\geq 50\%$ ) reduction from baseline to Week 8 in mean daily average pain score assessed by NRS (Sensitivity analysis)	mBOCF c	FAS	Fisher's exact test
Percentage of subjects achieving $\geq 30\%$ (or $\geq 50\%$ ) reduction from baseline to Week 8 in mean daily average pain score assessed by NRS where all subjects with missing Week 8 data are classified as non-responders (Sensitivity analysis)	BOCF	PPS	Fisher's exact test
Table continued on next page			

Variable	Imputation	Analysis Set	Analysis Type
Percentage of subjects achieving $\geq 30\%$ (or $\geq 50\%$ ) reduction from baseline to EOT in mean daily average pain score assessed by NRS	LOCF	FAS	Fisher's exact test
Change from baseline to Week 2, Week 4 and Week 8 for the FIQR function, symptoms and overall impact subscales	None	FAS	MMRM analysis of change from baseline a
Change from baseline to Week 8 for the FIQR function, symptoms and overall impact subscales (Sensitivity analysis)	Discontinuation-reason based multiple imputation b	FAS	MMRM analysis of change from baseline a
Change from baseline to Week 8 for the FIQR function, symptoms and overall impact subscales (Sensitivity analysis)	None	PPS	MMRM analysis of change from baseline a
Change from baseline to Week 8 for the FIQR function, symptoms and overall impact subscales (Sensitivity Analysis)	mBOCF c	FAS	ANCOVA analysis of change from baseline
Change from baseline to EOT for the FIQR function, symptoms and overall subscales	LOCF	FAS	ANCOVA analysis of change from baseline
Overall subject improvement assessed by PGIC at Week 2, Week 4 and Week 8	mBOCF c	FAS	Proportional odds model
Overall subject improvement assessed by PGIC at Week 2 and Week 4 (Sensitivity analysis)	LOCF	FAS	Proportional odds model
Overall subject improvement assessed by PGIC at EOT	LOCF	FAS	Proportional odds model

aMMRM analysis uses data from baseline and change from baseline data at Week 2, Week 4 and Week 8 time points.

bDiscontinuation-reason based multiple imputation (MI) will use a "Jump to Reference" algorithm (where placebo is the reference group) for subjects who discontinue due to lack of efficacy or AEs and standard regression-based MI for subjects with missing data for other reasons.

cmBOCF is defined as imputation by baseline observation carried forward for subjects who discontinue due to lack of efficacy or AEs, and imputation by LOCF for subjects with missing data at the specific analysis time point for other reasons.

The following secondary binary response endpoints (responder, non-responder; as defined in Section 6.1.2) will be analyzed using the Fisher's exact test for ASP8062 versus placebo:

- Percentage of subjects achieving  $\geq 30\%$  (or  $\geq 50\%$ ) reduction from baseline to Week 8 in mean daily average pain score assessed by NRS where all subjects with missing Week 8 data are classified as non-responders,
- Percentage of subjects achieving  $\geq 30\%$  (or  $\geq 50\%$ ) reduction from baseline to Week 8 in mean daily average pain score assessed by NRS where mBOCF is used to impute a responder status for subjects with missing Week 8 data, and
- Percentage of subjects achieving  $\geq 30\%$  (or  $\geq 50\%$ ) reduction from baseline to EOT in mean daily average pain score assessed by NRS.

Summary statistics will show the number and percentage of subjects who show response for each treatment group, 2-sided 90% CI for the percentage within each treatment group (ASP8062, placebo) calculated using the exact unconditional approach, difference in

percentages, 2-sided 90% CI for ASP8062 versus placebo calculated using the exact unconditional approach, and 1-sided p-value. In addition, the above responder analysis will be repeated in the PPS as a sensitivity analysis of the percentage of subjects achieving  $\geq 30\%$  (or  $\geq 50\%$ ) reduction from baseline to Week 8 in mean daily average pain score assessed by NRS where all subjects with missing Week 8 data are classified as non-responders.

The following secondary endpoints will be analyzed using the MMRM analysis as described in Section 7.4.1.1 for the primary efficacy analysis (however with only analysis time-points Week 2, Week 4 and Week 8 included):

- Change from baseline to Week 2, Week 4 and Week 8 for the FIQR function, symptoms and overall impact subscales (where no explicit imputation is performed).

For each endpoint, standard summaries of the MMRM analysis results will be provided, as described in Section 7.4.1.1. This will include an overlay plot. In addition, the MMRM analysis will be repeated in the PPS and also in the FAS under the assumption that data is MNAR using decision-reason based multiple imputation as sensitivity analyses of the change from baseline to Week 8 for the FIQR function, symptoms and overall impact subscales.

The following secondary endpoints will be analyzed using ANCOVA, as described in Section 7.4.1.2 for the second sensitivity analysis of the primary endpoint:

- Change from baseline to Week 8 in FIQR function, symptoms and overall impact subscale scores where mBOCF is used for imputation of missing data at Week 8. Modified baseline observation carried forward is defined as imputation by BOCF for subjects who discontinue due to lack of efficacy or AEs, and imputation by LOCF for subjects with missing data at Week 8 for other reasons.
- Change from baseline to EOT in FIQR function, symptoms, and overall impact subscale scores.

For each endpoint, standard summaries of the ANCOVA results, as described in Section 7.4.1.2 will be provided.

The following secondary endpoints will be analyzed using a proportional odds model for ordinal data including treatment group as a factor:

- Overall subject improvement assessed by PGIC at Week 2, Week 4 and Week 8 where mBOCF will be used for subjects with missing data,
- Overall subject improvement assessed by PGIC at Week 2 and Week 4 where LOCF will be used for subjects with missing data, and
- Overall subject improvement assessed by PGIC at EOT.

At each time point, the proportion of subjects in each treatment group achieving each level of response (1 = “Very Much Improved”, 2 = “Much Improved”, 3 = “Minimally Improved”, 4 = “No Change”, 5 = “Minimally Worse”, 6 = “Much Worse”, 7 = “Very Much Worse”), will be presented, together with the odds ratio, associated 90% CI based on profile likelihood and 2-sided p-value based on likelihood ratio test for ASP8062 vs placebo. The cumulative logit link will be used to specify the proportional odds model in SAS.

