### **Statistical Methods:**

#### **Sample size justification:**

The sample size calculations are based on the primary efficacy endpoint of change from baseline to Week 8 in mean daily average pain NRS. A meta-analysis of the change from baseline in mean daily average pain NRS for pregabalin or duloxetine vs placebo in studies for fibromyalgia indicated an effect size of approximately 0.30.

Using an effect size of 0.39 (30% larger than the meta-analysis result) for the primary efficacy endpoint for the comparison of ASP8062 vs placebo, 84 subjects in the ASP8062 and placebo groups would be required to provide 80% power to demonstrate statistical significance using a 1-sided 5% significance level (based on the assumption of normally distributed data, and taking into account the interim analysis for futility).

The total number of subjects required for the analysis would be 168 (84:84 subjects in ASP8062: placebo). Assuming approximately 5% of randomized subjects will not contribute to the analysis, then a total of 178 subjects would be required for randomization using a 1:1 randomization ratio (89:89 subjects for the ASP8062: placebo groups).

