### **7.4.2 Analysis of Secondary Endpoints**

The secondary efficacy endpoints are defined in [Section 2.3.2 Secondary Endpoints].

The primary analysis for the secondary endpoints of mean daily average pain score ( $\geq 30\%$  and 50% reduction from baseline to Week 8 and to EOT) will be carried out with the Fisher's Exact Test. For the Week 8 analysis, subjects with missing data will be classified as non-responders (BOCF) and an additional analysis will use mBOCF. For the EOT analysis, LOCF will be used.

The primary analysis for the change from baseline to Weeks 2, 4 and 8 for the FIQR subscales of Physical Function, Symptoms and Overall Impact will use the same MMRM analysis as described in [Section 7.4.1.1 Primary Analysis]. The primary analysis for the change from baseline to EOT for the FIQR subscales will use an ANCOVA model, with covariates of baseline FIQR subscale score and center. An additional ANCOVA analysis will be conducted at Week 8 with mBOCF for subjects with missing data.

The primary analysis for the PGIC will use the proportional odds model for ordinal data, with model term for treatment group. The analysis will be used to assess PGIC at Weeks 2, 4, 8 and EOT. For subjects with missing data, the analysis at Weeks 2, 4 and 8 will be conducted using imputation of 'No Change' for subjects who discontinue due to lack of efficacy or AEs,

and imputation by LOCF for subjects with missing data at Week 8 for other reasons. An additional analysis at Weeks 2 and 4 will use LOCF.

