#### 7.4.1.1 Primary Analysis of Primary Endpoint

The hypothesis for comparison of mean change from baseline between ASP8062 and placebo is shown below:

**H0:** The mean change from baseline to Week 8 in mean daily average pain score assessed by NRS (0 to 10 scale) for ASP8062 30 mg once daily group is same as (or higher, i.e., worse than) the placebo group.

**H1:** The mean change from baseline to Week 8 in mean daily average pain score assessed by NRS (0 to 10 scale) for ASP8062 30 mg once daily group is less than the placebo group.

The change from baseline in mean daily average pain score to Week 1, Week 2, Week 3, Week 4, Week 5, Week 6, Week 7 and Week 8 will be analyzed using a mixed-effect, repeated measures (MMRM) model including treatment, center (pooled where necessary), time (study Week 1 to 8), and treatment-by-time interaction as fixed effects, baseline mean daily average pain score and baseline mean daily average pain score-by-time interaction as covariates. The treatment group contrasts for change from baseline to Week 8 will be the primary statistical inference obtained from this model.

This analysis will utilize observed data, and there will be no imputation for missing data. Parameters will be estimated using restricted maximum-likelihood and the Kenward-Roger approximation will be used to estimate denominator degrees of freedom and adjust SEs.

An unstructured variance-covariance structure will be used to model the within-subject errors. If the fit of the unstructured covariance structure fails to converge, the following covariance structures will be tried in order until convergence is reached: heterogeneous Toeplitz (for efficacy endpoints captured in e-diary only, i.e. mean daily average pain score assessed by NRS [REDACTED] followed by compound symmetry.

Residual plots of scaled residuals will be used to check the fit of the model and assess whether there is any evidence of non-normality.

From the MMRM model the following results will be presented:

- Least squares (LS) mean estimates, SE and 2-sided 90% confidence interval (CI) for mean change from baseline to each analysis time-point (Week 1 to Week 8) within a treatment group (ASP8062, placebo),
- The difference in LS means for ASP8062 versus placebo, SE for the difference and 2-sided 90% CI for the difference at each analysis time-point,
- One-sided p-value for ASP8062 versus placebo at each analysis time-point, and

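### As written, the FIQR repeated-measures model adjusts for baseline pain instead of the FIQR subscale's own baseline; a short clarification would probably recover precision

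*SAP*

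**What the plan says.** SAP 7.4.1.1 defines the primary MMRM for change in daily pain, with "baseline mean daily average pain score and baseline mean daily average pain score-by-time interaction as covariates". SAP 7.4.2 then analyses the FIQR function, symptoms and overall impact subscales as follows: "MMRM analysis as described in Section 7.4.1.1 for the primary efficacy analysis (however with only analysis time-points Week 2, Week 4 and Week 8". The time points are the only stated departure. Protocol 7.4.2 does the same: it refers the FIQR analysis at Weeks 2, 4 and 8 back to the primary model and mentions no change of covariate.

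The ANCOVAs are worded differently. For FIQR at end of treatment, protocol 7.4.2 specifies a model "with covariates of baseline FIQR subscale score and center". Its next sentence, on the Week 8 mBOCF ANCOVA, names no covariate. In the SAP, both FIQR ANCOVAs point to 7.4.1.2, which refers only to a baseline value, in text about the primary endpoint. The protocol synopsis sends FIQR at end of treatment to the ANCOVA it has just described, and the covariate there is baseline pain NRS.

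**The concern.** FIQR function measures the first secondary objective, physical function. Change in a score usually depends strongly on that score's own baseline, so a model that omits it leaves explainable variance in the residual. Any chance difference between arms in baseline FIQR also stays in the treatment estimate. With dropout, the missing-at-random assumption would no longer condition on baseline FIQR.

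The cross-reference covers all three subscales and carries into the FIQR per-protocol and multiple-imputation runs. The jump-to-reference step in SAP 7.4.1.2 imputes from baseline values only, without saying which baseline applies when the endpoint is FIQR.

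**Working it through.** **1. The plan's own figure.** The documents size only the primary endpoint (protocol synopsis, sample size justification). The inputs are "Using an effect size of 0.39 (30% larger than the meta-analysis result"), "using a 1-sided 5% significance level", and "84 subjects in the ASP8062 and placebo groups would be required to provide 80% power".

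- n per arm = 2(1.645 + 0.842)² / 0.39² = 81.3, so 82. The stated 84 is two higher, and the text says it allows for the futility analyses. A two-sided 5% test would need 104, so the one-sided reading fits.
- With 5% not contributing, 84 / 0.95 = 88.4, so 89 per arm and 178 in total, as stated.
- Power at 84 per arm = Φ(0.39·√42 − 1.645) = Φ(0.883) = 81%.

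The sample size reproduces. No precision or power figure is given for FIQR.

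**2. Effect of the covariate.** With complete data, an unstructured covariance and baseline-by-time terms, the Week 8 MMRM contrast equals a Week 8 ANCOVA. Take equal baseline and Week 8 SDs, scaled to 1, and let

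- ρ = correlation of baseline FIQR with Week 8 FIQR,
- r = correlation of baseline pain with baseline FIQR,
- q = correlation of baseline pain with Week 8 FIQR.

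The residual variance of FIQR change is

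- adjusted for baseline FIQR: 1 − ρ²
- adjusted for baseline pain: 2(1 − ρ) − (q − r)²

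The second is larger whenever |q − r| < 1 − ρ. The two are equal at |q − r| = 1 − ρ, and beyond that the ordering reverses.

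**3. Numbers.** All correlations are assumptions; none is in the documents. Power is Φ(0.39·√42 / √ratio − 1.645). It supposes, for illustration only, 84 per arm and a FIQR effect of 0.39 residual SDs under the own-baseline model.

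| ρ | r | q | Own baseline | Baseline pain | Variance ratio | Power |
|---|---|---|---|---|---|---|
| 0.4 | 0 | 0 | 0.84 | 1.20 | 1.43 | 68% |
| 0.4 | 0.3 | 0.12 | 0.84 | 1.17 | 1.39 | 69% |
| 0.4 | 0.5 | 0.20 | 0.84 | 1.11 | 1.32 | 71% |
| 0.6 | 0.5 | 0.30 | 0.64 | 0.76 | 1.19 | 75% |
| 0.7 | 0.6 | 0.42 | 0.51 | 0.57 | 1.11 | 77% |
| 0.8 | 0.7 | 0.56 | 0.36 | 0.38 | 1.06 | 79% |
| 0.7 | 0.6 | 0.30 | 0.51 | 0.51 | 1.00 | 81% |
| 0.8 | 0.5 | 0.30 | 0.36 | 0.36 | 1.00 | 81% |

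Rows 2 to 6 set q = rρ, meaning that baseline pain predicts Week 8 FIQR only through baseline FIQR. They give 6% to 39% more variance. Row 1, with pain unrelated to FIQR, is the extreme at 43%. The last two rows relax q = rρ, and the loss disappears.

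**4. Simulation check.** With ρ = 0.6, r = 0.5, q = 0.3, 84 per arm and 5,000 runs, the variance ratio was 1.19. The mean estimate was −0.391 under both models against a true −0.39, so neither was biased.

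**The case against.** The strongest reply is that a fully literal reading proves too much. SAP 7.4.1.1 also fixes the response as change in pain, so the cross-reference already needs the endpoint substituted; a sensible programmer would substitute its baseline too. Other text points the same way:

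- The synopsis sends FIQR at end of treatment to the ANCOVA it has described for pain, while protocol 7.4.2 spells that analysis out with the FIQR baseline. Reference to an earlier model may therefore be shorthand for the endpoint's own baseline.
- SAP 7.4.1.1 limits one fallback covariance structure to e-diary endpoints, so it was written partly as a template for other endpoints.
- SAP 6.1 defines a FIQR baseline, and footnote a to SAP Table 19 mentions baseline data in a FIQR context.

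This makes the subscale baseline a likely intention, and it means the text does not show that the wrong model will be run. It does not supply the missing rule. SAP 7.4.2 lists its exception and leaves the covariate out, 7.4.1.1 names pain where the ANCOVA text is generic, and the Table 19 footnote names no covariate.

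A reader might also infer that the main MMRM and the mBOCF ANCOVA use different covariates and so cannot be compared. The documents do not establish this. The SAP's ANCOVA baseline is generic, and the protocol names baseline FIQR only for the end-of-treatment analysis. The per-protocol and imputation runs reuse the same MMRM, so their covariates match the main FIQR analysis whichever baseline is meant.

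**Conclusion.** The point stands as a specification gap worth closing. On the text as it is, the FIQR MMRM adjusts for baseline pain and not for baseline FIQR. The probable cost is precision: roughly 6% to 40% more variance in plausible cases (19% in a central case, or about 9% on the standard error), and none in edge cases. That range rests on assumed correlations, equal SDs and complete data.

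Two stronger conclusions should not be drawn. One is a definite loss in effective number of subjects: the documents hold no FIQR correlations or SDs, and any such count should start from the 168 planned for analysis, not the 178 randomized. The other is biased FIQR results: under randomization neither covariate biases the contrast in expectation, and what remains is unadjusted chance imbalance in baseline FIQR. The primary endpoint and the sample size are untouched.

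**What to change.** In SAP 7.4.2, state that the FIQR MMRM uses Weeks 2, 4 and 8, with the baseline value of the subscale being analysed and its interaction with time in place of baseline pain and its interaction. In the same edit:

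- apply this to the per-protocol and multiple-imputation FIQR runs, including the baseline used in the imputation step;
- state that the baseline value in the FIQR ANCOVAs (Week 8 mBOCF and end of treatment) is that same subscale baseline;
- reconcile the protocol synopsis with protocol 7.4.2 on the end-of-treatment ANCOVA covariate.

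The cost is a few sentences. FIQR is already collected at randomization and its baseline is defined in SAP 6.1, so no new data are needed. Making the change before database hard lock avoids choosing between two models after unblinding.

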### **5.3.1.4 Patient Global Impression of Change and Patient Global Impression of Severity**

The Patient Global Impression of Change (PGIC) and Patient Global Impression of Severity (PGIS) are adaptable global indices that capture the patient's perspective on a defined condition. The PGIC is a self-administered 7-pt Likert scale that asks subjects to evaluate their fibromyalgia relative to baseline. The PGIC is anchored by "very much improved" and "very much worse." The PGIS is a self-administered 6-pt Likert scale that asks subjects to evaluate how their fibromyalgia is now. The PGIS is anchored by "no symptoms" to "very severe".

Both the PGIC and the PGIS will be completed by the subject on the tablet device at the site. The PGIC will be completed at Weeks 2, 4, 8 and 10. The PGIS will be completed at Randomization, Weeks 2, 4, 8 and 10.

A high-contrast, black and white image showing a series of horizontal bars of varying lengths. The bars are mostly black, set against a white background. The lengths of the bars decrease from left to right. The image is heavily processed, appearing as a binary black and white pattern.

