### **3.3 Randomization**

All subject numbers will be assigned using the interactive response technology (IRT) starting at screening. All subjects will have a unique, ten-digit subject number. The first five digits of this number will be the investigator's site number. The second five digits assigned will represent the subject's accession number. This will be the number that identifies a subject during the course of the study.

Screening procedures, wash-out of prohibited medications (if applicable) and the baseline-diary run-in will be completed prior to randomization. Only subjects who meet all inclusion criteria and exhibit none of the exclusion criteria will be randomly assigned in a 1:1 ratio to ASP8062 30 mg or placebo according to the randomization schedule through IRT. The randomization will be stratified by site. Site personal will dispense the treatment according to the IRT system's assignment.

If a subject is assigned a randomization number, but does not receive study drug, the randomization number will not be used again.

The randomization schedules that determine subject treatment will be computer-generated by IRT before the beginning of the study. Specific procedures for randomization through the IRT are contained in the study-specific IRT manual.

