**Table 3 Derivation of mean daily average NRS pain score**

Analysis Time Point	Derivation
Baseline	Arithmetic mean of non-missing daily pain scores from the last 7 days prior to the randomization visit i.e., using the non-missing scores from Study Days -7 to -1. If the pain score is missing on all of these 7 days, then the score will be set to missing.
Treatment period Week 1, Week 2, Week 3, Week 4, Week 5, Week 6, Week 7, Week 8, EOT	Arithmetic mean of non-missing daily pain scores collected within time window per visit windows defined in Section 7.11.4.3 Table 26. If the pain score is missing on all of the days during the time window, then the score for that time point will be set to missing.
Follow-up period Week 10	

EOT: end of treatment

Change from baseline is defined in Section 7.1. A negative change indicates a reduction/improvement from baseline (i.e., a favorable outcome).

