	Total score	A normalization factor is applied to each of the three subscale scores: the function subscale score is divided by 3, the overall subscale score is divided by 1 (i.e. it is left unchanged), and the symptoms subscale score is divided by 2.  The total FIQR score is the sum of the three normalized subscale scores. The range of scores will be 0 to 100, with a lower score indicating a better response.

EOT: end of treatment

- Overall subject improvement assessed by PGIC at Weeks 2, 4, 8, and EOT.

[figure not shown]
The PGIC is a self-administered 7-point Likert scale that asks subjects to evaluate their fibromyalgia relative to baseline. This is a single question and the grade ranges from 1 to 7, where 1 anchors “Very Much Improved” and 7 anchors “Very Much Worse”. Subjects will complete the questionnaire during the clinic visits on a tablet device.

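### The PGIC proportional odds model has treatment as its only term although baseline pain and PGIS are collected; adding them would probably gain some power, by an amount the documents cannot fix

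*SAP*

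**What the plan says.** On the PGIC model the two documents agree. SAP 7.4.2: "The following secondary endpoints will be analyzed using a proportional odds model for ordinal data including treatment group as a factor", covering Weeks 2, 4, 8 and EOT. Protocol 7.4.2: "The primary analysis for the PGIC will use the proportional odds model for ordinal data, with model term for treatment group". The SAP reports an odds ratio, a 90% interval and a two-sided likelihood-ratio p-value. Under SAP 7.1 that p-value is judged at 0.10, which in the favourable direction equals a one-sided 5% test.

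Two baseline severity measures are available. SAP Table 3 defines baseline pain as: "Arithmetic mean of non-missing daily pain scores from the last 7 days prior to the randomization visit". Inclusion criterion 13 requires at least 5 of 7 run-in ratings. For PGIS, Protocol 5.3.1.4 says: "The PGIS will be completed at Randomization, Weeks 2, 4, 8 and 10". SAP Table 17 already tabulates both as baseline characteristics.

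The continuous endpoints are adjusted. The primary MMRM (SAP 7.4.1.1) uses "baseline mean daily average pain score and baseline mean daily average pain score-by-time interaction as covariates", plus pooled center. The modified-BOCF sensitivity analysis uses "ANCOVA with treatment group and center (pooled site) as fixed effects and baseline value as a covariate". The FIQR analyses take over both models by cross-reference. Neither document explains why PGIC is treated differently.

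**The concern.** In an ordinal logistic model, leaving out a prognostic baseline variable pulls the treatment log odds ratio toward zero and lowers power. Entry allows mean pain anywhere from 4 to 9, and randomization is stratified by site alone, so the arms can differ by chance in baseline severity. The MMRM and ANCOVA allow for such a difference; the PGIC odds ratio does not. PGIC also supports the stated secondary objective on overall subject status. At stake is the precision of one secondary endpoint, using data the trial already holds.

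**Working it through.** **1. The plan's own figure.** Inputs from the Protocol synopsis, sample size justification: effect size 0.39, one-sided 5%, 80% power, 5% not contributing, 1:1 allocation. All of this concerns pain NRS; no power is stated for PGIC.

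- n per arm = 2(1.645 + 0.842)² / 0.39² = 81.3, so 82. The plan gives 84 and says it allows for the futility interims.
- 84 / 0.95 = 88.4, so 89 per arm and 178 in total. This matches.

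**2. Assumptions not in the documents.** The latent PGIC effect is 0.39 SD (carried over from pain) or 0.37 SD. R² is the share of latent PGIC variance explained by baseline pain and PGIS, varied from 0 to 0.30.

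**3. Normal approximation, 89 per arm.** Power = Φ(0.39·√(89/2) / √(1 − R²) − 1.645).

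- R² = 0: 0.39 × 6.671 = 2.602; 2.602 − 1.645 = 0.957; power 83.1%.
- R² = 0.10: 2.602 / 0.949 = 2.742; 2.742 − 1.645 = 1.097; power 86.4%.

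**4. Simulation.** Seven-category proportional odds model, likelihood-ratio test at one-sided 5%, 89 per arm, treatment only versus treatment plus two correlated covariates. Set-up A: shift 0.39, 1,500 trials per row, Monte Carlo error about 1 point. Set-up B: shift 0.37, 1,000 trials per row, error about 1.2 points.

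| R² | Normal approximation, adjusted | A: unadjusted → adjusted | B: unadjusted → adjusted |
|---|---|---|---|
| 0 | 83.1% | 84.5% → 84.3% | 81.6% → 81.9% |
| 0.04 | 84.4% | 82.4% → 83.9% | 80.5% → 80.7% |
| 0.10 | 86.4% | 83.1% → 86.3% | 80.2% → 83.3% |
| 0.20 | 89.7% | 80.7% → 89.9% | 82.1% → 88.3% |
| 0.30 | 92.8% | 83.1% → 93.5% | not run |

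The unadjusted normal value is 83.1% throughout. A third set-up used one covariate and a shift of 0.37. Power rose from 81.6% to 83.8% at r = 0.2 (R² = 0.04), from 82.1% to 85.7% at r = 0.3 (0.09) and from 78.9% to 84.8% at r = 0.4 (0.16), with error about 1.3 points.

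Taking these together, the gain is about 0 points at R² = 0, 0 to 2 at 0.04, about 3 at 0.10 and 6 to 9 at 0.20. The 9 comes from set-up A, where the unadjusted 80.7% lies below the 83.1% expected, so the upper end may be partly noise.

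**5. Test size.** With two covariates: 5.4% unadjusted and 5.4% adjusted (2,000 trials). With one covariate: 5.4% and 5.6% (3,200 trials, error 0.4). Adding pooled-center indicators, for an assumed 14 or so centers, gave 6.0% (1,500 trials, error 0.6) in one run and about 7% in another.

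**The case against.** The treatment-only model is pre-specified, is the same in both documents and has adequate size. It is not an error.

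PGIC "asks subjects to evaluate their fibromyalgia relative to baseline". It is already a rating of change with no baseline of its own, so its link to baseline severity may be weak. The 4-to-9 entry range narrows one of the covariates further. The documents give no correlation and no PGIC effect size. A reader might infer that power is demonstrably being lost; the documents do not support that, because R² = 0 is compatible with everything they say.

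Two further strong readings also fail. PGIC is not the only unadjusted secondary analysis, since the 30% and 50% pain responders are compared by Fisher's exact test. Nor does it carry the overall-status objective alone, since the FIQR subscales serve it too, with baseline adjustment. SAP 7.4.3 and 7.8 are redacted, so an adjusted PGIC analysis elsewhere cannot be excluded; the point applies to 7.4.2 only.

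Adjustment is also not free: it changes the target to a conditional odds ratio and needs a rule for missing baselines.

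All of this limits the size and wording of the point. None of it shows that adjustment would do harm. The absence of a baseline PGIC explains why there is no such term, but not why no baseline severity covariate is used.

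**Conclusion.** The point holds as a modest efficiency improvement. Power is probably, not demonstrably, given up: nil to about 3 points for R² up to 0.10, and 6 to 9 points only if R² reaches 0.20. These figures rest on an assumed latent effect of 0.37 to 0.39 SD, 89 analysed per arm, proportional odds, and an R² that the documents do not supply. If the covariates prove uninformative, no measurable power is lost and size is unchanged. The choice introduces no bias, and the primary endpoint, the sample size and every stated power figure stand as they are.

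**What to change.** Before unblinding, amend SAP 7.4.2 as follows.

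- Add two covariates to the PGIC proportional odds model at Weeks 2, 4, 8 and EOT: baseline mean daily average pain NRS and baseline PGIS. State how PGIS is coded; a linear score uses one parameter.
- Give a simple rule for a missing baseline, such as the overall mean, so that no FAS subject is dropped.
- Keep the treatment-only odds ratio as a supportive result.
- State in the table footnote that the adjusted odds ratio is conditional on baseline and is not directly comparable with the unadjusted one.
- Record the departure from the Protocol 7.4.2 model in the SAP revision history.

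Site is also absent from the PGIC model, although "The randomization will be stratified by site". Pooled-center indicators should not be added, given the test sizes above. A van Elteren test stratified by pooled center is optional and not part of this fix.

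The cost is SAP wording, two model terms and one additional supportive line in the table. No new data are needed.
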